9.2.2 Administration of AxMP

The IRT will assign the required AxMP (TCS) kit numbers for each subject at each dispensing visit. The TCS will be provided as mometasone furoate, 0.1% cream in kit sizes of 180–225 g Q2W. If needed, additional TCS kit(s) may be dispensed to the subject at a scheduled or unscheduled visit at the investigator's discretion. The amount of additional TCS dispensed must be recorded in the eCRF.

Subjects will be instructed to apply a thin film of the dispensed TCS (Europe: Class 3 [potent]) once daily to active lesions, as needed. The TCS should be discontinued when control is achieved; discontinuation should preferably be gradual and the maximum duration of treatment should not exceed 3 weeks. The safety and appropriateness of continued or repeated courses of TCS therapy will be monitored and supervised by site staff.

From randomisation (Week 0) and until last administration (at Week 24), the TCS will be dispensed and the subject must return used and unused TCS tubes at each subsequent trial visit, to assess the amount of medication used. The subjects must be instructed by the site staff on the importance of returning all used and unused TCS tubes. The site staff will return used and unused TCS tubes to the contract manufacturing organisation (CMO). The TCS tubes will be weighed at the CMO before shipment to the trial sites and again upon return.

An additional, lower potency TCS or TCI may be used at the investigator's discretion on areas of the body where use of the supplied TCS is not advisable such as areas of thin skin (face, skin fold areas, genital areas, etc.) or on areas where continued treatment is considered unsafe. The lower potency TCS and TCI will not be provided by LEO and will not be weighed, but must be registered in the eCRF as concomitant medications (see Section 9.6).

Further details on TCS dispensing are provided in the trial product handling manual. TCS administration must be carried out according to these instructions.

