9.8 Treatment logistics and accountability

9.8.1 Labelling and packaging of trial products

Investigational medicinal product

The IMP will be packaged in individually numbered kits, each containing 1 syringe (tralokinumab 150 mg or placebo). Primary and secondary packaging materials (syringe and outer carton, respectively) will be individually labelled.

The labelling of IMPs will be in accordance with Annex 13, local regulations, and trial requirements. Label text will be translated into local languages, as required.

Auxiliary medicinal product

The AxMP (TCS) will be packaged in individually numbered kits that contain tubes of TCS cream with a total weight of 180–225 g. Primary and secondary packaging materials (tube and outer kit carton, respectively) will be individually labelled.

The labelling of AxMPs will be in accordance with Annex 13, local regulations, and trial requirements. Label text will be translated into local languages, as required.

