9.8.3 Drug accountability

Trial product accountability will be performed in the IRT.

IMP accountability

The investigator is fully responsible for the IMPs at the trial site and for maintaining adequate control of the IMPs and for documenting all transactions with them. Dispensing of IMPs may be delegated, e.g., to a hospital pharmacy, as locally applicable.

Individual drug accountability of the IMP administered to each subject randomised in the trial must be documented. The individual drug accountability must be available during monitoring visits and will be checked by the CRA to verify correct dispensing of the IMP. Drug accountability information will be entered in the IRT, where also inventory status of all IMP at the trial site will be maintained. For more information about IMP and AxMP accountability, please refer to the trial product handling manual.

The IMPs must be fully accounted for by the CRA with the help of site staff responsible for dispensing the IMPs. All unused IMPs supplied by the CMO on behalf of LEO will be returned to the CMO.

AxMP accountability

The number of TCS tubes returned by the subject must be documented in the eCRF by the trial staff. The subject will at each dispensing visit return used, partly used, and unused TCS tubes (including empty kit cartons) to the site. Once reconciled and accounted for, the site will return all of the above to the CMO. For further details, please see the trial product handling manual.

All returned AxMP tubes will be weighed by the CMO to determine the amount of TCS used by the subject. The detailed procedure for weighing of AxMP tubes and subsequent transfer of tube weight data to the clinical database will be documented.

Reporting in eCRF

The IMP kit numbers as well as the date and time of IMP administration will be recorded in the eCRF. In addition, the site of IMP injection should be given. For AxMP (TCS), the kit/tube number, date of dispensation and return, and number of tubes dispensed and returned will be recorded in the eCRF.

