#### Amount of TCS used

The amount of TCS used will be calculated as specified in section 6.6.8 and analysed in two ways, reflecting the two consumption assumptions. The primary analysis will be using the most conservative assumption that all missing tubes were fully used. The second assumption will be used as a sensitivity analysis, reflecting the primary analysis’s extreme opposite, that all non-returned tubes were not used. The method used for analysis will be the one specified in the protocol. Additionally, descriptive histograms of both consumption assumptions will be produced.

In an extra sensitivity analysis, the amount of TCS used will be log transformed. This transformation has in a similar trial proven to fit data better. TCS amount will be log transformed by adding 1 (due to potential zero values) and then taking the logarithm. The analysis will use the same repeated measures model with the mean modelled as follows:

$$\log[\text{TCS amount used} + 1] (g) = \text{Treatment} * \text{visit} + \text{prior CSA use} + \text{country} + \text{Baseline IGA}$$

The analysis results will be presented by back-transforming using the exponential function, thus producing estimated geometric means and estimated ratio of means, which will be presented with nominal p-values and 95% confidence intervals (CI). This sensitivity analysis will be done for both consumption assumptions.

Additionally, descriptive histograms of both consumption assumptions will be produced for the amount of TCS.

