### 6.6.8 Drug accountability

For each subject, the weight of TCS used for a given visit interval (WGTUSED) will be calculated as the difference between the weight of the tubes dispensed (WGTDISP) and the weight of the returned tubes (WGTRET):

- if  $WGTRET \leq WGTDISP$  then  $WGTUSED = WGTDISP - WGTRET$
- if  $WGTRET > WGTDISP$  then  $WGTUSED = 0$ .

When tubes are not returned as specified in the protocol, the following rules will be applied:

- If tubes are returned at the wrong visit, the amount of TCS used from these tubes will be assumed to be used in the period from the tubes being dispensed to being returned.
- If a dispensed tube is not returned at all and the subject remains in the study, two different approaches will be applied to explore two extreme assumptions:
  1. It will be assumed, conservatively, that the missing tube has been fully used by the subject in the period between the date the tube was dispensed, and the date of the

next subsequent visit attended by the subject. Estimated content (100 g) for the kit number will be used as a contribution to the WGTRET.

2. It will be assumed that the missing tube has not been used at all by the subject in the period between the date the tube was dispensed, and the date of the next subsequent visit attended by the subject, i.e. contribution from the tube to the WGTRET is set to 0.
- In the case where tubes from the last dispensing visit are not returned due to the subject being withdrawn from the trial, the amount of TCS used from these tubes will not be calculated (i.e. set to missing).
  - If dispensed tubes have no weighing data due to any other cause the most conservative estimate will be imputed, i.e. that the whole tube dispensed was used.

If a subject does not attend a planned visit, daily usage (DAYUSE) is calculated for the period between the tubes being dispensed and the subsequent dispensing visit, i.e.

$DAYUSE = WGTUSED / DURATION$  where  $DURATION = ENDDATE$  (date of the subsequent dispensing visit) -  $STARTDATE$  (date of the tubes being dispensed). If all tubes in the batch are not dispensed/returned at the same time, date of the first dispensed or last returned tube in the batch is used, dependent on the situation. The amount of the TCS used for each visit in the period (missing visit(s) and the first visit after the tubes being dispensed) is calculated by multiplying daily usage (DAYUSE) by the number of days between the visit and the previous visit.

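### The SAP's rule for unreturned TCS tubes uses a 100 g content with no clear unit and adds it to the wrong side, so the 'fully used' and 'not used' analyses come out reversed

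*SAP*

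**What the plan says.** SAP 6.6.8 calculates TCS use in a visit interval as "the difference between the weight of the tubes dispensed (WGTDISP) and the weight of the returned tubes (WGTRET"), with use set to 0 if the returned weight exceeds the dispensed weight.

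The rule at issue starts "If a dispensed tube is not returned at all and the subject remains in the study". Two opposite assumptions follow. The first is that the missing tube was fully used, and here the SAP states: "Estimated content (100 g) for the kit number will be used as a contribution to the WGTRET". The second is that it was not used at all, and here the "contribution from the tube to the WGTRET is set to 0".

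SAP 6.6.5 (Amount of TCS used) assigns their roles: "The primary analysis will be using the most conservative assumption that all missing tubes were fully used". The 'not used' assumption is the sensitivity analysis, and a log-transformed sensitivity analysis is run under both.

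The protocol describes the supply. Section 9.8.1 has "individually numbered kits that contain tubes of TCS cream with a total weight of 180–225 g". Section 9.2.2 says: "The TCS tubes will be weighed at the CMO before shipment to the trial sites and again upon return". Section 9.8.3 has the eCRF record "the kit/tube number, date of dispensation and return, and number of tubes dispensed and returned".

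**The concern.** Two things look wrong in the same sentence of the SAP.

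First, the content figure. The rule is about a tube, but the 100 g is attached to a kit number, and the protocol's numbered kits hold 180–225 g. Two programmers could reasonably implement this differently.

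Second, the sign. Anything added to the returned weight lowers calculated use. Adding an estimated content for a tube assumed empty, and nothing for a tube assumed untouched, runs against both assumptions.

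At stake is the pair of analyses meant to bracket TCS consumption. If the code follows the text, the analysis labelled most conservative shows roughly the minimum use and its sensitivity analysis shows the maximum. Unreturned tubes are foreseeable: under the COVID-19 addendum (Protocol Appendix 8, section 4), TCS for several visits could be handed out or couriered at once.

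**Working it through.** **Inputs**

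- Use = WGTDISP − WGTRET, floored at 0 (SAP 6.6.8).
- Contribution of a missing tube to WGTRET: 100 g under 'fully used', 0 under 'not used' (SAP 6.6.8).
- Kit content: 180–225 g in several tubes (Protocol 9.8.1).
- Tubes per kit, k: not given in either document. Values 1 to 6 are shown as an assumption.

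**Step 1: which unit does 100 g fit?**

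Read per kit, it falls short by 180 − 100 = 80 g to 225 − 100 = 125 g (44% to 56% of content).

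Read per tube, content is 180/k to 225/k:

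| k | Content per tube (g) | Does 100 g fit? |
|---|---|---|
| 1 | 180–225 | no |
| 2 | 90–112.5 | yes |
| 3 | 60–75 | no |
| 4 | 45–56.25 | no |
| 5 | 36–45 | no |
| 6 | 30–37.5 | no |

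With k = 2, a flat 100 g overstates content by up to 10 g (100 − 90) or understates it by up to 12.5 g (112.5 − 100). With k = 3 to 6 it overstates content by 25 g (100 − 75) to 70 g (100 − 30).

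**Step 2: which way do the contributions act?**

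Illustrative case: a two-tube kit with W g per tube, one tube returned with 40 g left, the other missing. Known use from the returned tube is W − 40. The intended results are:

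- 'Fully used': (W − 40) + W = 2W − 40.
- 'Not used': W − 40.

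The SAP as written gives:

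- 'Fully used': 2W − (40 + 100) = 2W − 140.
- 'Not used': 2W − (40 + 0) = 2W − 40.

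| W (g) | Intended 'fully used' | Intended 'not used' | SAP 'fully used' | SAP 'not used' |
|---|---|---|---|---|
| 90 | 140 | 50 | 40 | 140 |
| 100 | 160 | 60 | 60 | 160 |
| 112.5 | 185 | 72.5 | 85 | 185 |

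The order is reversed at every weight. At W = 90 g, the SAP's 'fully used' result (40 g) is below the use actually measured on the returned tube (50 g).

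**Step 3: would a better number alone repair it?**

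No. At W = 100 g, putting the measured tube weight where the 100 g now stands still gives 60 g for 'fully used' and 160 g for 'not used'. Putting a kit content there gives 200 − (40 + 180) = −20, floored to 0 g, and likewise 0 g for 200 or 225 g.

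**Step 4: would reversing the contributions alone repair it?**

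Only half. 'Fully used' would then add 0 and need no content figure. 'Not used' would still carry the flat 100 g:

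- k = 2: 40 g instead of 50 g at W = 90, and 85 g instead of 72.5 g at W = 112.5.
- Illustrative 4 × 50 g kit, three tubes returned with 60 g left in total, one missing: 200 − (60 + 100) = 40 g, although 150 − 60 = 90 g was measured as used.
- Per-kit reading, whole kit missing: 80–125 g recorded as used instead of 0.

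Both changes are therefore needed.

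**The case against.** The strongest reply is that this is loose drafting with an obvious intent. The rule is about tubes, the 100 g is called an estimate, and two 100 g tubes make a 200 g kit, inside the protocol's range. If WGTRET is a slip for the weight used, then 100 g for 'fully used' and 0 for 'not used' point the right way.

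The first part stands. The 100 g cannot be called wrong without a tube count, which the documents do not give.

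The second part stands only as a guess at intent. It also needs a step the SAP does not state: removing the missing tube from WGTDISP, because dispensed minus returned already counts it as used. At W = 100 g with that step, 'fully used' is (100 − 40) + 100 = 160 g, as intended. Without it, the result is (200 − 40) + 100 = 260 g, more than was dispensed. And on this reading the flat 100 g sits in the primary analysis, giving 50 + 100 = 150 g instead of 140 g at W = 90 and 72.5 + 100 = 172.5 g instead of 185 g at W = 112.5.

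It is also fair to say that the endpoint is minor. It is listed under 'other' endpoints (Protocol section 6, Panel 4), and the hierarchy in Protocol 14.3.6 covers only primary and secondary endpoints.

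**Conclusion.** The point holds in this form: the 100 g has no defined unit and is unnecessary, and the WGTRET contributions as written reverse the two assumptions. The reversal follows from the SAP's own formula and does not depend on tube size. In the worked case it exchanges 160 g and 60 g, a 100 g shift for one missing tube. The two-tube kit and the 40 g remainder are illustrative.

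The error in the content figure depends on the reading: at most 10–12.5 g per tube with two tubes per kit, 25–70 g per tube with three to six, and 80–125 g if 100 g means a kit.

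A reader might infer two stronger claims that the documents do not support:

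- That 100 g is simply a wrong content figure. The rule is per tube, and 100 g is compatible with a two-tube kit.
- That the tralokinumab–placebo difference in TCS use is biased by a known amount. No non-return rate is given, and home-use supply is described without distinction by arm in a blinded trial. Differential non-return is possible but not shown.

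Alpha, power and the confirmatory tests are unaffected. What changes is which of the two TCS-use estimates carries the primary label, and whether they bracket actual use.

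**What to change.** Amend SAP 6.6.8, both parts together:

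1. Drop the flat 100 g. Use the missing tube's own dispensed weight as recorded before shipment, or the labelled content of that tube if the weight is missing.
2. State the contribution for each assumption. Under 'fully used' the tube adds 0 to WGTRET, so its whole dispensed content counts as used. Under 'not used' it adds its dispensed weight to WGTRET, so 0 g counts as used.

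In the worked 200 g kit this gives 160 g and 60 g. The SAP should also say whether recorded weights include the empty tube. If they do, the packaging of a tube assumed fully used must not be counted as cream.

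The cost is SAP wording and a check of the derivation code before unblinding. No new data are needed, provided the pre-shipment weights can be traced through the recorded kit/tube numbers.

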### 6.6.9 Descriptive statistics

In support of all endpoints, summaries will be included for all observed scores by visit.

## 6.7 Analysis of safety

As specified in the protocol, the analysis of safety will be based on the safety analysis set and the safety follow-up analysis set.

### 6.7.1 Adverse Events

Adverse events (AEs) will be summarised and listed. However, the summaries will be split into the two periods, the treatment period and the safety follow-up period. This is to differentiate the AEs based on whether or not subjects are on active treatment.

The start date of the COVID-19 pandemic is defined in Section 6.8.2.

#### Assignment of AEs to periods

An AE will be assigned to a given period (treatment or safety follow-up) if the start date of the AE is after the start date and before or at the end date of that period (see Section 6.8.2, Table 6).

For AEs with start day on the same day as the first dose was given, only AEs starting after the first dose was given will be considered treatment emergent and assigned to the treatment period.

For the handling of incomplete start dates of AEs, see Section 6.8.3.

#### Sort order of AE tables

Generally, AE tables by system organ class and/or preferred term will be sorted by decreasing number of affected subjects:

- For the treatment period, AE tables will be sorted by decreasing number of affected subjects in the Tralokinumab Q2W+TCS group. AEs only occurring in the Placebo+TCS group will be sorted last by decreasing number of affected subjects in the Placebo+TCS group.
- For the safety follow-up period, AE tables will be sorted by decreasing total (whole trial period) number of affected subjects in the Tralokinumab Q2W+TCS group. AEs only occurring in the Placebo+TCS group will be sorted last by decreasing number of affected subjects in the Placebo+TCS group.

## 6.7.2 Vital signs

Vital signs will be summarised and listed.

For the summary tables of vital signs by visit, the last pre-dose vital sign assessment will be presented. If no dosing occurs at a visit, the last assessment recorded at the visit will be presented.

For the first 3 IMP dosing visits, subjects will be monitored after IMP administration for immediate drug reactions for a minimum of 30 minutes with vital signs taken every 30 minutes or until stable, these measurements will be listed.

## 6.7.3 ECG

ECG data will be summarised and listed for the treatment period. ECG data from the safety follow-up period will be listed.

The overall central evaluation of ECG will be presented using shift tables for the treatment period.

## 6.7.4 Laboratory data

Laboratory data will be summarised and listed.

For the laboratory values, if the value is below the lower limit of quantification, half of the lower limit will be used for quantitative summaries. If the value is above the upper limit of quantification, the upper limit value will be used.

If more than one laboratory value is reported for the same visit and time point, the latest value will be used in summary statistics and analyses.

Potentially clinically significant values will be defined as displayed in [Table 3](#).

**Table 3: Potentially clinically significant biochemistry and haematology values**

Protocol Lab parameter	SI Unit	PCS low	PCS High
Biochemistry			
Sodium	mmol/L	< 129 mmol/L, < 125 mmol/L	> 160 mmol/L
Potassium	mmol/L	< 3 mmol/L, < 2.5 mmol/L	> 6.5 mmol/L, > 7.5 mmol/L
Creatinine	umol/L	N/A	> 1.5xULN, > 3xULN

Trial ID: LP0162-1346	Date: 21-OCT-2020	Version: v1.0 Page 22 of 35
-----------------------	-------------------	--------------------------------

Protocol Lab parameter	SI Unit	PCS low	PCS High
Calcium	mmol/L	< 1.9 mmol/L	> 3.0 mmol/L, > 3.5 mmol/L
Alkaline phosphatase	U/L	N/A	> 3xULN
Aspartate aminotransferase	U/L	N/A	> 3xULN, > 5xULN, > 10xULN, > 20xULN
Alanine aminotransferase	U/L	N/A	> 3xULN, > 5xULN, > 10xULN, > 20xULN
Bilirubin	umol/L	N/A	> 2xULN
Cholesterol	mmol/L	N/A	> 6.2 mmol/L
LDL cholesterol	mmol/L	N/A	> 4.1 mmol/L, > 4.9 mmol/L
HDL cholesterol	mmol/L	N/A	> 1.6 mmol/L
Triglycerides	mmol/L	N/A	> 2.3 mmol/L, > 5.6 mmol/L
Glucose (non-fasting)	mmol/L	< 3.9 mmol/L	>11.1 mmol/L
Haematology			
Haemoglobin	g/L	<110 g/L, < 80 g/L	> 185 g/L for male, > 165 g/L for female
Neutrophils, absolute count	10  /L	< 1.5 10  /L, < 1.0 10  /L, < 0.5 10  /L	N/A
Lymphocytes, absolute count	10  /L	< 1.0 x 10  /L, < 0.5 x 10  /L	> 5.0 x 10  /L
Monocytes, absolute count	10  /L	< 0.1 x 10  /L	> 0.8 x 10  /L
Eosinophils, absolute count	10  /L	N/A	> 1.5, > 5.0
Basophils, absolute count	10  /L	N/A	> 0.2
Thrombocytes	10  /L	< 100 x 10  /L, < 30 x 10  /L, < 10 x 10  /L	> 450 x 10  /L

PCS: potentially clinically significant; ULN: Upper limit of normal, i.e. upper limit of normal reference range.

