14.3.13.3 Clinical laboratory evaluation

The change in each of the laboratory parameters from baseline to each visit will be summarised by visit and treatment group as mean, standard deviation, median, 1st quartile, 3rd

quartile, minimum, and maximum values for the safety analysis set. Laboratory parameters will be listed for the safety follow-up analysis set.

Laboratory parameters will be classified as 'low', 'normal' or 'high', depending on whether the value is below, within, or above the reference range, respectively. A shift table will be produced showing the categories at baseline against those at end of treatment. Subjects with laboratory parameters outside the reference range will be listed.

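### SAP Table 3 marks only high HDL cholesterol as potentially clinically significant, so the HDL flag points at the wrong tail and can never mark a low value

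*SAP*

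**What the plan says.** SAP Section 6.7.4 makes Table 3 the definition: "Potentially clinically significant values will be defined as displayed in" that table. Its columns are "Protocol Lab parameter SI Unit PCS low PCS High", and the footnote expands the abbreviation: "PCS: potentially clinically significant; ULN: Upper limit of normal".

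The HDL row is "HDL cholesterol mmol/L N/A > 1.6 mmol/L". Read against the headers, no low value is ever PCS, and any value above 1.6 mmol/L is.

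The neighbouring lipid rows have the same shape: "Cholesterol mmol/L N/A > 6.2 mmol/L" for total cholesterol and "LDL cholesterol mmol/L N/A > 4.1 mmol/L, > 4.9 mmol/L" for LDL. Triglycerides likewise have N/A on the low side and limits only on the high side.

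HDL is in the chemistry panel of Protocol Panel 10, so the rule will be applied to trial data. Neither document explains the interest in high HDL or sets a low HDL limit anywhere.

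**The concern.** For total cholesterol, LDL and triglycerides, a high value is the unfavourable direction, and a high-only limit makes sense. HDL runs the other way: the recognised concern is a low value. This is ordinary knowledge of the measure and does not come from the protocol or SAP. The row looks as if HDL was carried along with the other lipids.

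What is at stake is the meaning of one safety flag. PCS limits exist to pick out values of possible concern. For HDL they would pick out values not usually of concern. If treatment lowered HDL, the PCS flags could not show it. If treatment raised HDL, PCS flags would increase without an obvious safety reason.

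**Working it through.** There is no stated figure to reproduce. The check is a reading of the table, a comparison with other rows, and a search for other handling of HDL.

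**1. Is the row what the SAP intends, or a conversion fault?** The row has all four cells (name, unit, low, high). The entry carries a greater-than sign and sits in the high column. A low limit displaced by text conversion would carry a less-than sign. The row is therefore the SAP's own content.

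**2. Does the table format force a high-only rule?** No.

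| Parameter in Table 3 | Low limit | High limit |
|---|---|---|
| Total cholesterol | none | > 6.2 mmol/L |
| LDL | none | > 4.1 and > 4.9 mmol/L |
| Triglycerides | none | > 2.3 and > 5.6 mmol/L |
| HDL | none | > 1.6 mmol/L |
| Sodium, potassium, calcium, glucose | set | set |
| Neutrophils | set | none |

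Neutrophils already have the low-only shape that HDL would need.

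**3. What the rule does.** An HDL of 1.7 mmol/L is PCS, because 1.7 > 1.6. No low HDL, however extreme, is PCS, because the low cell is N/A.

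**4. Where a low HDL is still seen.**
- Protocol Section 14.3.13.3 summarises change from baseline for each laboratory parameter by visit and treatment group, including quartiles, minimum and maximum.
- The same section classifies each value "depending on whether the value is below, within, or above the reference range".
- It adds: "A shift table will be produced showing the categories at baseline against those at end of treatment". Subjects with out-of-range values are also listed.
- SAP Section 6.7.4 keeps the laboratory summaries and listings.
- Protocol Section 11.4.4.2 has the investigator judge the clinical significance of every central-laboratory result outside the reference range.

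**5. How many subjects might be flagged (illustration only).** The documents give no HDL mean, SD or reference range. Assume a normal distribution and a value for all 250 planned subjects at a visit. The proportion flagged is 1 − Φ((1.6 − mean)/SD).

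| Assumed mean, SD (mmol/L) | z | Proportion above 1.6 | Of 250 |
|---|---|---|---|
| 1.3, 0.35 | 0.30/0.35 = 0.857 | 0.196 | 49 |
| 1.4, 0.40 | 0.20/0.40 = 0.50 | 0.309 | 77 |
| 1.6, 0.40 | 0/0.40 = 0 | 0.50 | 125 |

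The last row is 50% simply because the assumed mean equals the cut-off. The range shows that flags could be frequent; it does not estimate how frequent. The number flagged for low HDL is zero under any distribution.

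**The case against.** The strongest reply is that little is lost. A reader might infer from Table 3 that the trial's safety reporting would miss a fall in HDL. The documents do not support that: the outputs in step 4 above all show low HDL, and investigators must review it when it is out of range. This part of the reply stands, and it confines the point to the PCS flags.

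A reader might also infer that a rise in HDL would be presented as a safety signal, or that large numbers of subjects would be counted as abnormal. The documents do not support that either. Section 6.7.4 defines PCS values but specifies no PCS count table, no comparison between arms and no action that follows from a flag. High-HDL flags unrelated to treatment would arise in both randomised arms, so they would mainly add noise to a descriptive output.

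Third, the direction of concern for HDL is not stated in the documents, and the sponsor may have a reason for watching high values. That is possible, but no reason is given, and such an interest would not explain the missing low limit.

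The reply does not rescue the row itself. The reference-range outputs sit beside the PCS flag and do not correct it. The shift table compares only baseline with end of treatment. Whether PCS values are tabulated or only listed, the HDL flag selects the wrong tail.

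**Conclusion.** The HDL row of Table 3 is wrong as written, at minor severity. The flag marks values above 1.6 mmol/L and can mark no low value. The effect stops at the PCS flags: no endpoint, estimand, hypothesis test or error rate uses them, and low HDL remains visible elsewhere in the planned safety reporting.

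The conclusion rests on one premise from outside the documents, that low HDL is the direction of concern. It does not rest on the illustrative counts, which depend wholly on assumed distributions and should not be used to argue for greater severity.

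**What to change.** Before unblinding, change the HDL row of SAP Table 3 in one of two ways:

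- set the high cell to N/A and enter a low limit with the sponsor's justification; or
- if high HDL is deliberately of interest, state why and add a justified low limit beside the high one.

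The documents give no basis for a particular low cut-off, so the sponsor should choose it. A limit placed exactly at the laboratory's lower reference limit would only repeat the existing low category. The table's limits tied to the upper reference limit are multiples of it, from 1.5 to 20 times, so a PCS flag is evidently meant to mark more than an out-of-range value.

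The cost is one pair of table cells and one programming rule. No new data are needed. SAP Section 4 places the SAP before unblinding, which is the right time for the change.
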